## STATEMENT OF COMPLIANCE

The trial will be conducted in accordance with International Conference on Harmonisation Good Clinical Practice (ICH GCP) and the applicable United States (US) Code of Federal Regulations (CFR). The Principal Investigator will assure that no deviation from, or changes to the protocol will take place without prior agreement from the sponsor and documented approval from the Institutional Review Board (IRB), except where necessary to eliminate an immediate hazard(s) to the trial participants. All personnel involved in the conduct of this study have completed Human Subjects Protection and ICH GCP Training.

The protocol, informed consent form(s), recruitment materials, and all participant materials will be submitted to the IRB for review and approval. Approval of both the protocol and the consent form must be obtained before any participant is enrolled. Any amendment to the protocol will require review and approval by the IRB before the changes are implemented to the study. All changes to the consent form will be IRB approved; a determination will be made regarding whether a new consent needs to be obtained from participants who provided consent, using a previously approved consent form.

## 1 PROTOCOL SUMMARY

### 1.1 SYNOPSIS

**Title of the Study:** Use of Platelet Rich Plasma after Arthroscopic Debridement for Triangular Fibrocartilage Complex Tears

**Number of Subjects:** 48

**Objective:** The objective of this study is to determine if treatment with platelet rich plasma (PRP) after arthroscopic debridement of triangular fibrocartilage complex (TFCC) tears improves patient outcomes when compared to those who were not treated with PRP after arthroscopic debridement.

**Methodology:** 48 subjects with TFCC tears will be randomized to treatment with PRP versus placebo (normal saline). Subjects and medical staff outside of the operating room will be blinded to treatment group throughout the study. Outcome measures will include pain scale scores, grip strength, wrist range of motion, Patient-rated Wrist Evaluation (PRWE) scores, and Modified Mayo Wrist scores.

**Visit Schedule:** Pre-operative visit, post-operative visits at month 1, month 3, month 6 and year 1.

**Diagnosis and Main Inclusion Criteria for Inclusion/Exclusion:** Subjects with TFCC tears.

**Inclusion Criteria:**

- Male or Female >18 years of age
- TFCC tear requiring surgical intervention
- Be willing to undergo arthroscopic debridement and injection with PRP
- Be in good health other than the TFCC tear
- Have realistic expectations of surgical results
- Understand and be willing to follow all aspects of the study protocol and have signed and dated the IRB-approved Informed Consent Form and the Authorization for Use and Release of Health and Research Study Information (HIPAA) form prior to any study-related procedures being performed

**Exclusion Criteria: To be eligible for enrollment, the subject must not:**

- Have collagen-vascular, connective tissue, or bleeding disorders
- Be a smoker or have smoked in last 2 months
- Have any disease, including uncontrolled diabetes, which is clinically known to impact wound healing ability
- Have regional sympathetic dystrophy
- Be pregnant, lactating or expecting to be within the next 24 months
- Currently have an alcohol/substance abuse problem or have had a relapse within one year to screening visit
- Have an abscess or infection at the time of surgery
- Have a condition or be in a situation that, in the Investigator's opinion, may put the subject at significant risk, may confound the study results, or may interfere significantly with the subject's participation in the study

**Duration of the Study:** Subjects will be followed for 12 months post arthroscopic debridement.

**Criteria for Evaluation:** The primary outcome measure is the difference in improvement between preoperative and post-operative outcomes as measured by pain scale scores, grip strength, wrist range of motion, Patient-rated Wrist Evaluation (PRWE) scores, and Modified Mayo Wrist scores between patients treated with PRP and patients not treated with PRP after arthroscopic debridement. Pain scale scores, grip strength, wrist range of motion, PRWE scores, and the Modified Mayo Wrist Score will be measured at the pre-operative visit, and post-operatively at month 1, month 3, month 6, and year 1.

[figure not shown]
**Statistical Methods:**

A sample size of 48 subjects (24 in the treatment group and 24 in the control group) will provide sufficient information to produce descriptive summaries of study outcome endpoints and to perform exploratory analyses.

The purpose of this study is to explore surgical outcomes after treatment with platelet rich plasma (PRP) in patients undergoing arthroscopic debridement for triangular fibrocartilage complex (TFCC) tears. We hypothesize that use of PRP after arthroscopic debridement will result in a clinically significant reduction in pain and improved functional outcomes compared to arthroscopic debridement alone, as measured by pain scale scores, grip strength, wrist range of motion, Patient-rated Wrist Evaluation (PRWE) scores, and the Modified Mayo Wrist Score.

**Schedule of Visits and Procedures:** As depicted in Section 1.2.

## 1.2 SCHEMA

## 2 INTRODUCTION

### 2.1 ABBREVIATIONS AND TERMS:

PRP Platelet Rich Plasma  
 TFCC Triangular Fibrocartilage Complex  
 PRWE Patient-rated Wrist Evaluation

## 2.2 BACKGROUND AND CLINICAL RATIONALE FOR DATA REVIEW

Tears of the triangular fibrocartilage complex (TFCC) often result in ulnar sided wrist pain, decreased grip strength, and functional impairment. Treatment options include conservative management with immobilization, open repair, and arthroscopic repair versus debridement with or without ulnar shortening. The reported success rates after treatment, regardless of technique, are mixed. indicating the need for new treatment modalities.

New studies have emerged that support the use of platelet rich plasma (PRP) in the treatment of cartilage injuries and joint inflammation. Randomized controlled trials demonstrate that the use of PRP in patients with hip and knee osteoarthritis decreases pain and improves function. A pilot study by Loibl et al. showed similar results in basilar joint arthritis. Molecular studies reveal that PRP significantly increases the proliferation of chondrocytes, anabolic factors (TGF-B1) and antiinflammatory cytokines (IL-4, IL-10, IL-13) while decreasing inflammatory enzymes (COX-2) and proteinases (MMP3, MMP13, ADAMTS-5, IL-6). As such, PRP may be beneficial in the treatment of patient's with TFCC tears.

## 3 STUDY OBJECTIVES

The objective of this study is to compare outcomes and functionality measures of subjects treated with platelet rich plasma (PRP) after arthroscopic debridement of triangular fibrocartilage complex (TFCC) tears to subjects treated with arthroscopic debridement alone.

## 4 STUDY DESIGN

### 4.1 OVERALL DESIGN

Forty-eight (48) subjects with TFCC tears will be randomized to treatment with PRP versus placebo (normal saline). Subjects and medical staff outside of the operating room will be blinded to treatment group throughout the duration of the study. Outcome measures will include pain scale scores, grip strength, wrist range of motion, Patient-rated Wrist Evaluation (PRWE) scores, and Modified Mayo Wrist scores.

### 4.2 STUDY STRUCTURE

This is a randomized controlled trial, blinded to the subjects and medical support staff.

#### 4.3 DURATION

Subjects will be followed for 12 months post arthroscopic debridement. Their postoperative pain scale scores, grip strength, wrist range of motion, Patient-rated Wrist Evaluation (PRWE) scores, and Modified Mayo Wrist scores (measured at month 1, month 3, month 6, and year 1 postoperatively) will be compared to their preoperative scores. And the difference in improvement of the outcomes will be compared between treatment and control subjects. Study visits will coincide with standard clinical course visits including: pre-operative visits and follow-up visits at month 1, month 3, month 6 and year 1 post-operatively.

#### 4.4 STUDY QUESTIONNAIRES/ASSESSMENT

The patients of [name] eligible to participate in the study will proceed with outcomes data collection once study consents have been signed and the patient has been enrolled in the study.

#### 4.5 VISITS & PROCEDURES

Enrolled subjects will undergo baseline questionnaires/assessments and baseline imaging during their pre-operative visit. Once arthroscopic debridement is complete, patients will be randomized intraoperatively to treatment with PRP versus placebo (normal saline). Subjects and medical staff outside of the operating room will be blinded to treatment group throughout the study. Questionnaires/assessments will then be administered and performed at month 1, month 3, month 6 and year 1 post-operative visits. Follow-up imaging will be performed at 6 month post-operative visit.

### 5 STUDY POPULATION CHARACTERISTICS

#### 5.1 NUMBER OF SUBJECTS

Forty-eight (48) subjects undergoing arthroscopic debridement for TFCC tears will be randomized intraoperatively to treatment with PRP (24 subjects) versus treatment with normal saline (24 subjects).

## 5.2 STUDY POPULATION CHARACTERISTICS

Subjects who meet the inclusion/exclusion criteria detailed below will be enrolled into the study.

## 5.3 INCLUSION CRITERIA

- Male or Female >18 years of age
- TFCC tear requiring surgical intervention
- Be willing to undergo arthroscopic debridement and injection with PRP
- Be in good health other than the TFCC tear
- Have realistic expectations of surgical results
- Understand and be willing to follow all aspects of the study protocol and have signed and dated the IRB-approved Informed Consent Form and the Authorization for Use and Release of Health and Research Study Information (HIPAA) form prior to any study-related procedures being performed

## 5.4 EXCLUSION CRITERIA PROCEDURES

- Have collagen-vascular, connective tissue, or bleeding disorders
- Be a smoker or have smoked in last 2 months
- Have any disease, including uncontrolled diabetes, which is clinically known to impact wound healing ability
- Have regional sympathetic dystrophy
- Be pregnant, lactating or expecting to be within the next 24 months
- Currently have an alcohol/substance abuse problem or have had a relapse within one year to screening visit
- Have an abscess or infection at the time of surgery
- Have a condition or be in a situation that, in the Investigator's opinion, may put the subject at significant risk, may confound the study results, or may interfere significantly with the subject's participation in the study

## 6 VISITS & PROCEDURES

### 6.1 PRE-SCREENING & VISITS

The physician's appointment calendar will be pre-screened of potential study candidates who would be eligible for arthroscopic debridement. No study related data will be collected/administered until patient has signed consent and HIPAA.

### 6.1.1 PROCEDURES FOR FINAL STUDY ENTRY

A subject is considered “enrolled” when he/she has signed the IRB-approved consent form and HIPAA authorization in the presence of the Investigator, who will then collect and record the subject’s demographic information and medical history.

### 6.1.2 PRE-OPERATIVE VISITS

The subject will be screened in accordance with the inclusion/exclusion criteria and medical history collected. Pre-operative visual pain analogue score measurements, grip strength and wrist range of motion measurements, and Patient-rated Wrist Evaluation (PRWE) scores and Modified Mayo Wrist scores will be collected. Subject health information (e.g., demographics, general health), physical examination, medical photography, and hand imaging (see section 6.2) will be performed at screening.

### 6.1.3 FOLLOW-UP VISITS

Subjects will be required to attend post-operative visits at month 1, month 3, month 6 and at year 1. Review of medical records, physical examination, and medical photography will be conducted at all post-operative visits. At month 1, month 3, month 6, and year 1 visual pain analogue score measurements, grip strength and wrist range of motion measurements, and Patient-rated Wrist Evaluation (PRWE) scores and Modified Mayo Wrist scores will be collected. Medical imaging (Section 6.2) will be performed at month 6 post-operatively.

## 6.2 STANDARD OPERATIVE PROCEDURES

Standard Imaging: PA, lateral, and oblique X-ray views of the wrist and MR Arthrogram will be obtained pre-operatively and 6 months post-operatively. Medical photographs of the hand and wrist will be taken at each visit and on the day of the procedure.

Standard Surgical Procedure: The affected wrist is placed in a traction tower and arthroscopy is performed in standard fashion. A blunt trocar is placed through the 3/4 portal and a probe is used through the 4/5 portal. The wrist is then inspected for evidence of injury including the central and peripheral portions of the TFCC. An ArthroCare device is then inserted into the 4/5 portal, and the frayed TFCC is coblated.

### 6.3 RESEARCH RELATED PROCEDURES

Research Related Procedures: Once the arthroscopic debridement is complete, the patient is randomized to receive wrist injections of normal saline (placebo) or PRP (treatment group). The PRP is then obtained from patients assigned to the treatment arm (~9 cc of venous blood) and processed using the CASCADE Autologous Platelet System, a product made commercially available by the Musculoskeletal Transplant Foundation (MTF). Once processed, the PRP is injected into the debrided wrist.

### 6.4 MEDICAL IMAGING (STANDARD OF CARE)

A copy of any medical imaging results (e.g., hand radiology) collected during the study duration will be included in the study file. Imaging of the hand will consist of 3 X-ray views including PA, lateral and oblique views and an MR Arthrogram. Imaging will be completed pre-operatively and post-operatively at month 6.

### 6.5 INSTRUCTIONS FOR THE SUBJECTS

There are no special instructions for the subjects beyond those typically provided for hand surgery and in the informed consent. Subjects will be asked to complete research related questionnaires and assessments as indicated in section 6.1.3.

### 6.6 UNSCHEDULED VISITS

Each time the subject returns to the study site the Investigator will solicit and record information about any concurrent procedures or AEs as applicable though not anticipated.

## 7 STUDY INTERVENTION DISCONTINUATION AND PARTICIPANT DISCONTINUATION/WITHDRAWAL

### 7.1 EARLY DISCONTINUATION OF SUBJECTS

Each subject reserves the right to withdraw from the study at any time without jeopardy to her future medical care. All follow-up assessments and procedures

should be performed at the final study visit. For any subject who discontinues from the study, the date and reason for discontinuation will be recorded.

If a subject fails to return for one or more scheduled study visits, the Investigator will attempt to contact the subject to determine and document the reason the subject has failed to return and to encourage compliance with the study visit schedule.

A subject may be discontinued from the study for the following reasons:

- Subject did not undergo arthroscopic debridement as it was deemed not warranted by the Investigator
- Since enrollment in the study, subject has had alternative treatment that would otherwise affect the study questionnaire/outcomes data
- Subject does not complete scheduled follow-up visits per protocol
- Subject has died

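### Section 7.1 lets a randomised subject leave the study for having other treatment or missing visits, and nothing provides for their remaining visits through year 1

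*Combined protocol and SAP*

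**What the plan says.** Section 7.1 opens its list with "A subject may be discontinued from the study for the following reasons". Of the four reasons, two matter here: "Since enrollment in the study, subject has had alternative treatment that would otherwise affect the study questionnaire/outcomes data" and "Subject does not complete scheduled follow-up visits per protocol". The other two are that debridement was not performed and that the subject died.

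The same section has three safeguards. Follow-up assessments and procedures "should be performed at the final study visit". The date and reason for discontinuation are recorded. When a visit is missed, the Investigator is asked to get in touch, note why, and then "encourage compliance with the study visit schedule".

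Sections 4.5 and 6.3 place randomisation in the operating room after debridement. On the PRP arm, "Once processed, the PRP is injected into the debrided wrist". No repeat injection is described. Section 6.1.1 defines enrolment as signing the consent form and HIPAA authorisation, which comes before surgery. Section 4.3 plans 12 months of follow-up, with visits at months 1, 3, 6 and year 1. Section 9.1 excludes discontinued subjects from the data analysis, and section 9 rules out imputation.

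**The concern.** Once the injection has been given there is no study treatment left to stop, so discontinuation after randomisation means that follow-up ends. A subject who has a further wrist procedure at month 4 may be taken off and assessed once on exit, with no provision for the month-6 and year-1 assessments. A subject who misses month 3 may be taken off although willing to attend later, because no number of missed visits is stated.

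The first reason is defined by its effect on the outcome data. It is an inference, though a reasonable one, that subjects with persistent pain are those who seek other treatment. If PRP works as section 9.3 hypothesises, more of them would be on saline. Removing them improves the apparent saline result and shrinks the observed difference. A corrected analysis population cannot use scores that were never collected.

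**Working it through.** **The plan's own figure.** Section 9.6 uses a PRWE difference of 15, SD 18, two-sided 5% and 80% power. The normal approximation gives n = 2 × (1.960 + 0.842)² × 18² / 15² = 22.6, so 23 per arm; the t-test version gives 23.6, so 24. The stated 24 per arm reproduces. Enrolment is also 24 per arm, so there is no allowance for loss: t-test power is 80.7% at 24 per arm and 78.9% at 23.

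**Illustration of outcome-related removal.** From section 9.6: SD s = 18 and difference 15. Assumed, because the documents give no such figures: normal year-1 PRWE scores (higher is worse) with mean m = 35 on saline and 20 on PRP, and removal of subjects scoring above a threshold T.

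With z = (T − m)/s, the fraction above T is P = 1 − Φ(z). If all of them are removed, the mean of those kept is m − s × φ(z)/Φ(z). For T = 50:

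- Saline: z = 15/18 = 0.833, P = 0.2023, lost 24 × 0.2023 = 4.9. Mean kept = 35 − 18 × 0.2819/0.7977 = 28.64.
- PRP: z = 30/18 = 1.667, P = 0.0478, lost 24 × 0.0478 = 1.1. Mean kept = 20 − 18 × 0.0995/0.9522 = 18.12.
- Observed difference: 28.64 − 18.12 = 10.5, against 15.

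If only a fraction f of those above T is removed, the mean kept is (m − f × P × A)/(1 − f × P), where A = m + s × φ(z)/P is the mean of those above T (60.08 on saline, 57.47 on PRP). For f = 0.5 this gives 32.18 − 19.08 = 13.1.

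| Setting | Observed difference |
|---|---|
| T = 50, all removed | 10.5 |
| T = 50, half removed | 13.1 |
| T = 50, a quarter removed | 14.1 |
| T = 50, a tenth removed | 14.7 |
| T from 40 to 60, all removed | 8.1 to 12.6 |
| T from 40 to 60, half removed | 12.8 to 13.9 |
| T = 50, all removed, SD 20.5 (upper end in section 9.6) | 9.9 |
| T = 50, all removed, SD 6.6 (lower end in section 9.6) | 14.8 |

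**What full follow-up would show.** Retained scores would include the effect of the other treatment. If that treatment lowered PRWE by an assumed 15 points in those above 50, the difference under full follow-up would be 15 − 15 × (0.2023 − 0.0478) = 12.7. The part due to removal is then 12.7 − 10.5 = 2.2 points, not 15 − 10.5 = 4.5.

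**Direction.** If the arms have the same distribution and the rule is applied alike, removal takes equal shares on average and does not bias the difference. The pull towards no difference arises when PRP works. Uneven use of the rule between arms could move the result either way.

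**The case against.** The strongest reply is that the rule is optional and partly mitigated. The lead-in says only that a subject may be discontinued, an exit assessment is called for, and study visits coincide with standard clinical visits (section 4.3), with grip and motion entered in the medical record (section 8.3). Some later data could therefore exist even for a discontinued subject. This stands, and it limits the likely size. It does not remove the point: an optional rule without criteria can be applied unevenly, one exit assessment does not replace the month-6 and year-1 scores, and PRWE and pain are collected on study paper forms.

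Several stronger readings are tempting, and the documents do not support them:

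- That both reasons arise only after randomisation. The alternative-treatment reason runs from enrolment, so it also covers the interval between consent and surgery, where removal does not affect a randomised comparison.
- That section 7.1 contradicts itself on missed visits. Contact and encouragement can come first, and discontinuation later if visits remain incomplete. What is missing is a threshold.
- That an unblinded Investigator decides. The lead-in names no decision-maker; only the debridement reason mentions the Investigator. Section 10.2 gives the Investigator overall responsibility, which is not the same statement.
- That other treatment goes unrecorded. Sections 6.6 and 12.3.1 already call for concurrent procedures to be recorded.

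It is also fair to object that the illustration removes subjects on their own year-1 score, whereas removal would follow earlier symptoms. Imperfect correlation between the two would weaken the bias.

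**Conclusion.** The concern holds in a limited form. Section 7.1 permits, but does not require, follow-up of randomised subjects to end for reasons plausibly related to outcome, and no text provides for their remaining scheduled visits. This can bias the comparison, probably towards no difference if PRP works.

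A reader might take the fall from 15 to 10.5 as a forecast. It is an upper-end illustration for that threshold: it rests on assumed means, a normal distribution and removal of every subject above 50, and it is set against a difference that full follow-up would not wholly recover. With a quarter or a tenth removed, the difference is 14.1 or 14.7. The documents give no rate of other treatment or of discontinuation, so the actual size is unknown.

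This should be fixed, but it is not a fatal flaw. The certain loss, exclusion of discontinued subjects from analysis, comes from section 9.1. The distinct contribution of section 7.1 is data that may never be collected.

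**What to change.** - In section 7.1, for randomised subjects, remove alternative treatment and incomplete visits as reasons for leaving the study. State that every randomised subject is invited to all remaining visits through year 1 unless they withdraw consent or die.
- Keep the reasons that arise before randomisation: debridement not performed, and alternative treatment between consent and randomisation.
- Record the date and type of any further wrist treatment, building on the recording of concurrent procedures in sections 6.6 and 12.3.1.
- Amend section 9.1 to match. Otherwise it would still exclude subjects discontinued for any remaining reason, whatever had been collected.

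The cost is a short protocol amendment and visits that are already planned; the sample size does not change. The downside is that some late scores will include the effect of other treatment, which the recorded dates and types allow the report to describe.

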## 8 OUTCOME MEASURES AND SUMMARY OF METHODS OF DATA COLLECTION

### 8.1 OUTCOME MEASURES

#### 8.1.1 PRIMARY OUTCOME MEASURE

The primary outcome measure is the difference in improvement between preoperative and post-operative pain scale scores, grip strength, wrist range of motion, Patient-rated Wrist Evaluation (PRWE) scores, and Modified Mayo Wrist scores between patients treated with PRP and patients not treated with PRP after arthroscopic debridement.

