## 9 STATISTICAL PROCEDURES

Every attempt will be made to collect complete data and limit the occurrence of missing data. Due to the descriptive nature of all analyses, no imputation of missing data will be performed. Descriptive summaries will be based on all observations available within each of the relevant analysis populations.

Descriptive statistics will be presented for key outcome measures.

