### 9.2 COLLECTION AND DERIVATION OF PRIMARY AND SECONDARY OUTCOME MEASURES

### 9.2.1 PRIMARY OUTCOME MEASURES

The primary outcome measure is the difference in improvement between preoperative and post-operative pain scale scores, grip strength, wrist range of motion, Patient-rated Wrist Evaluation (PRWE) scores, and Modified Mayo Wrist scores between patients treated with PRP and patients not treated with PRP after arthroscopic debridement.

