### 9.3.1 PRIMARY OUTCOME MEASURE ANALYSIS

The primary outcome measure is the difference in improvement between preoperative and post-operative pain scale scores, grip strength, wrist range of motion, Patient-rated Wrist Evaluation (PRWE) scores, and Modified Mayo Wrist scores between patients treated with PRP and patients not treated with PRP after arthroscopic debridement.

Preoperative and postoperative outcome measures will be analyzed using descriptive statistics, including n, mean, standard deviation, median, minimum, maximum, and skewness.

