## 9.5 EXPLORATORY ANALYSES

The difference in preoperative versus postoperative outcomes within groups (treatment versus placebo) will be tested for significance using paired t-tests. The significance of differences in preoperative versus postoperative outcomes between groups (treatment and placebo group) will be analyzed using 2-sample t-tests. Additional analyses of possible relationships between outcomes may also be performed using appropriate inferential tests.

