## 9.6 SAMPLE SIZE CALCULATION

The trial will be powered to detect a difference in post-treatment PRWE scores between groups of 15, deemed to be clinically significant by the investigators. The standard deviations for PRWE scores previously published after treatment for TFCC tears ranges from 6.6 to 20.5. To detect a mean difference in post-treatment PRWE score of 15 points ( $SD = 18$ ) with a two-sided significance level of 5% and power of 80% with equal allocation to two arms would require 24 patients in each arm of the trial.

Subjects will be assessed per standard of care of their clinical requirement and qualification for surgery and upon subject's decision to participate in the study. The difference in preoperative and postoperative outcomes will be analyzed to

determine which group has the most improvement based on the following outcomes: pain scale scores, wrist range of motion, PRWE scores, and Modified Mayo Wrist scores.

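### Section 9.6 states 80% power at two-sided 5% for a PRWE comparison, but no section makes that comparison the primary analysis or designates a primary outcome and visit

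*Combined protocol and SAP*

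**What the plan says.** **Sample size.** The first paragraph of section 9.6 says "The trial will be powered to detect a difference in post-treatment PRWE scores between groups of 15". It takes SD 18, a two-sided 5% level, 80% power and equal allocation, and arrives at 24 per arm. On variability it says "The standard deviations for PRWE scores previously published after treatment for TFCC tears ranges from 6.6 to 20.5". It gives no baseline SD and no pre/post correlation.

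**Primary outcome.** Sections 8.1.1, 9.2.1 and 9.3.1 share one definition, which begins "The primary outcome measure is the difference in improvement between preoperative and post-operative pain scale scores, grip strength, wrist range of motion" and also covers PRWE and the Modified Mayo score. There is no ranking, composite or multiplicity rule. Section 8.1.3 lists the same five measures as exploratory, and the secondary sections are marked not applicable.

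**Visits.** Section 4.3 lists months 1, 3, 6 and year 1, and says improvement will be compared between the arms. None of these visits is designated primary.

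**Analysis.** Under 9.3.1 the primary measures "will be analyzed using descriptive statistics, including n, mean, standard deviation, median, minimum, maximum, and skewness". Section 9 says "Due to the descriptive nature of all analyses, no imputation of missing data will be performed". The between-arm test appears under Exploratory Analyses (9.5): "The significance of differences in preoperative versus postoperative outcomes between groups (treatment and placebo group) will be analyzed using 2-sample t-tests". The second paragraph of 9.6 also works with change ("The difference in preoperative and postoperative outcomes will be analyzed to" identify the group that improves more) and lists four outcomes, omitting grip strength.

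**Purpose.** The synopsis justifies 48 subjects by descriptive and exploratory aims. The synopsis and section 9.3 both also state a hypothesis that PRP is superior.

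**The concern.** A power statement means something only for a named test on a named outcome at a named time. Here the test that was sized (post-treatment PRWE between arms) is not the primary analysis, and the test that is specified (change scores, in principle for every outcome) is neither primary nor the one that was sized.

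If the trial is meant to be confirmatory, nothing in the plan says which of five outcomes and four visits decides whether PRP worked, so that choice could be made after the results are known and no result is protected at 5%. If it is meant to be exploratory, the power statement and the superiority hypothesis suggest a level of evidence that the analysis sections do not offer. A reader cannot tell which applies.

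**Working it through.** **1. The plan's own figure.** Inputs from 9.6: difference 15, SD 18, two-sided 0.05, n = 24 per arm. Two-sample t-test, noncentrality = 15 / (18 × √(2/24)) = 15 / 5.196 = 2.887, 46 df, critical value 2.013. Power = **80.7%**. Solving for n at 80% gives 23.60, so 24 per arm. The stated sample size reproduces.

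**2. Where that test sits in the plan.**

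| Element | Sized in 9.6, first paragraph | Primary (8.1.1, 9.2.1, 9.3.1) | Between-arm test (9.5) |
|---|---|---|---|
| Outcome | PRWE | five measures, unranked | not restricted |
| Quantity | post-treatment score | improvement | pre/post difference |
| Visit | not named | none designated | none designated |
| Method | two-sided 5%, 80% power | descriptive statistics | 2-sample t-test |
| Status | basis of sample size | primary | exploratory |

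No column joins the sized quantity, a test and primary status.

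**3. Does the 9.6 power carry over to the 9.5 test?** Change-score SD = √(18² + s0² − 2 × r × 18 × s0), with baseline SD s0 and pre/post correlation r both assumed. For s0 = 18 and r = 0.3: √(324 + 324 − 194.4) = 21.3. Power at 24 per arm for a difference of 15:

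| Assumed s0 | r = 0.3 | r = 0.5 | r = 0.7 |
|---|---|---|---|
| 15 | 73.4% | 86.1% | 97.3% |
| 18 | 66.6% | 80.7% | 95.4% |
| 20.5 | 60.4% | 74.7% | 92.1% |

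The change-score SD equals 18 when r = s0 / (2 × 18), that is 0.42, 0.50 or 0.57 for the three rows. The value 15 has no source in the documents, and 20.5 is the top of the post-treatment range reused as a baseline value.

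**4. False-positive chance if any nominal p<0.05 were taken as success.** Simulation with no true effect: normal data, 24 per arm, equal correlation between measures or visits (assumed), 1,000,000 trials per setting.

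| Family of tests | Assumed correlation | At least one p<0.05 | At least one favouring PRP |
|---|---|---|---|
| Five measures, one visit | 0 / 0.3 / 0.5 / 0.7 | 22.7 / 21.0 / 18.4 / 15.0% | 11.9 / 10.6 / 9.2 / 7.5% |
| PRWE, four visits | 0.3 / 0.5 / 0.7 / 0.8 | 17.4 / 15.7 / 13.2 / 11.5% | 8.8 / 7.8 / 6.6 / 5.8% |

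Check at independence: 1 − 0.95⁵ = 22.6%. A single test has 5%, or 2.5% favouring PRP. The two families use different correlation grids, so their ranges should not be compared with each other.

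**5. Power of a single PRWE test after losses.** Section 5.1 gives 24 per arm as the number randomised, and 9.6 has no allowance for loss over 12 months. Losses of 2/24 = 8% and 4/24 = 17% are assumed. ANCOVA uses SD = 18 × √(1 − r²) with 2n − 3 df; at r = 0.3 this SD is 17.17.

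| Evaluable per arm | Unadjusted t-test | ANCOVA, r = 0.3 |
|---|---|---|
| 24 | 80.7% | 84.2% |
| 22 | 77.0% | 80.8% |
| 20 | 72.8% | 76.7% |

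**The case against.** The best defence is that the study is openly exploratory. The synopsis says its purpose is to explore, section 9 calls every analysis descriptive, and the tests are filed under exploratory analyses. On that reading no protected claim is intended and the error rates in step 4 describe nothing the trial will assert. This has weight: it is why an exploratory repair stands level with a confirmatory one below. It does not remove the contradiction, because 9.3 and 9.6 state a superiority hypothesis and a powered test.

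A second defence is that 9.6 makes PRWE primary by implication. No section says so. Even if it is inferred, the visit, and the choice between post-treatment score and change, stay open.

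Stronger readings that a reader might infer are not supported:

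- **That no visits are named or no between-arm comparison is planned.** Section 4.3 names four visits and plans the comparison, and 9.5 commits to t-tests. What is missing is a designated primary outcome and visit.
- **That 24 per arm is miscalculated.** It reproduces.
- **That naming PRWE leaves 80% power intact.** It does so for the unadjusted test only if all 48 randomised subjects are evaluable.

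**Conclusion.** The concern holds and should be fixed before any by-arm review of outcome data. The 5% and 80% in 9.6 attach to no planned primary test, and the plan does not settle which outcome and visit carry the conclusion. This rests on the text alone.

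The size of the consequence depends on assumptions. The false-positive ranges of 15% to 23% and 11.5% to 17.4% apply only if an efficacy claim is made on any nominally significant result. Power for the 9.5 test is 67%, 81% or 95% at assumed correlations of 0.3, 0.5 or 0.7 with an assumed baseline SD of 18, so the 9.6 figure cannot simply be transferred to it.

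**What to change.** Two options of equal standing; the sponsor should state which purpose the trial has.

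**(a) Confirmatory.**
- In 8.1.1, 9.2.1 and 9.3.1, name PRWE at one sponsor-chosen visit as the single primary outcome, fixed before any by-arm review of outcome data.
- Move its between-arm comparison from 9.5 to 9.3.1 as the one two-sided 5% test, with an estimate and 95% confidence interval. Adjustment for the baseline PRWE already collected is preferable; it targets the same 15-point difference.
- Make the other four measures secondary and the other PRWE visits supportive. Align the synopsis, 8.1.3, the descriptive wording in section 9 and the second paragraph of 9.6.
- State in 9.6 that 24 per arm gives 80% power for the unadjusted test only if all are evaluable, and restate the power for the expected loss. This fix does not itself require a larger sample.
- State the analysis population and missing-data handling for this test, and reconcile them with 9.1, which makes per protocol the primary group and excludes discontinued subjects.

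**(b) Exploratory.** Remove the power and hypothesis-test language from 9.3 and 9.6, align the hypothesis in the synopsis, report all outcomes with confidence intervals, and make no efficacy claim.

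**Cost.** Either option is a protocol amendment, which the Statement of Compliance requires the IRB to approve before use. Under (a) four outcomes lose primary status and the stated power may become slightly less favourable. Under (b) the sponsor gives up an efficacy claim. Neither needs new data.
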